6.2.1.6 Vasodilators

Use of vasodilators and infusion dose will be recorded. Examples of vasodilators include nitroprusside, nitroglycerin, and nicardipine

Use of vasodilators will be recorded from first use following separation from bypass, until the subject is discharged from the hospital or at Day 28.

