Length of Time on Vasodilators

Length of time on vasodilators will be measured from first use following separation from bypass, until the subject is discharged from the hospital or at Day 28. The length will be derived as the time in hours from separation from CPB until discontinuation of all vasodilators. Any duration of re-use of vasodilators will continue to accrue. If a subject did not use any vasodilators the length is set to 0. As a sensitivity analysis, subjects with no use of vasodilators

Asklepion GROWTH HEALTH INNOVATION

11 August 2017

will be excluded. For subjects who died before discharge from the hospital or before Day 28, respectively, the observed length of time on vasodilators will be used. As sensitivity analyses subjects who died will (1) be excluded from analysis and (2) be assigned a length of time on vasodilators of 28 days.

For the length of time on vasodilators the same analyses as described for the primary endpoint will be applied.

Length of Hospitalization

The length of hospitalization will be calculated as the total number of days postoperative until discharge from the hospital. For subjects who died before discharge from the hospital or before Day 28, respectively, the observed length of hospitalization will be used. As sensitivity analyses subjects who died will (1) be excluded from analysis and (2) be assigned a length of hospitalization of 28 days.

For the length of hospitalization, the same analyses as described for the primary endpoint will be applied.

Thoracotomy Output - Duration and Volume of Chest Tube Drainage:

The total postoperative duration (in hours) that the chest tube is used will be calculated as the time from the end of the surgery to the time the chest tube is removed. If an additional chest tube is required or reinserted (until discharge from the hospital or at Day 28) the duration that the additional chest tube was used (from time of insertion to time of removal) will be added to the time the original chest tube was used for the total postoperative duration. If a subject did not use any chest tube the duration is set to 0. As a sensitivity analysis, subjects with no use of chest tube will be excluded. For subjects who died before discharge from the hospital or before Day 28, respectively, the observed duration of chest tube drainage will be used.

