4.4 Efficacy Analysis

4.4.1 Analysis of Primary Efficacy Variable

The primary efficacy endpoint is a composite variable consisting of the longer of either (1) length of time on mechanical ventilation or (2) length of time of inotrope use.

The definition of mechanical ventilation shall include invasive mechanical ventilation or non-invasive mechanical ventilation including BPAP or CPAP. The definition of inotrope use includes medications which are considered within the derivation of the total inotrope score (dopamine, dobutamine, milrinone, epinephrine, phenylephrine, norepinephrine).

The length of time on mechanical ventilation will be measured until the subject is discharged from the hospital or at Day 28. The length will be derived as the time in minutes from separation from CPB (variable "End time" of parameter "CPB" from section "Post incision" on CRF "Surgery") until discontinuation of all mechanical ventilation including non-invasive support (variables "Stop Time/Date of last use of non-invasive ventilation" and "Stop Time/Date of last use of invasive ventilation" of parameter "CPB" from section "Post incision" on CRF "Mechanical ventilation"). If invasive or non-invasive mechanical ventilation is stopped but has to be restarted, time will continue to accrue by subtracting the total duration of all ventilation breaks (variables "Stop date/time" and "Restart date/time" from CRF "Ventilation breaks").

- Length of time on mechanical ventilation (min) =
(Time mechanical ventilation discontinuation - End time (CPB) + 1) -
sum of all ventilation breaks with any ventilation break = Restart time - Stop time + 1

If a subject did not receive any mechanical ventilation the length is set to 0. For subjects who died before discharge from the hospital or before Day 28, respectively, the observed length of time on mechanical ventilation will be used. As sensitivity analyses subjects who died will (1) be excluded from analysis and (2) be assigned a length of time on mechanical ventilation of 28 days.

Length of time of inotrope use will be measured until the subject is discharged from the hospital or until Day 28, whichever occurs first. The length will be derived as the time in minutes from separation from CPB (variable "End time" of parameter "CPB" from section "Post incision" on CRF "Surgery") until last use (last "end date/time" of any medication as documented in section "Inotropes" on CRF "Inotropes and Vasoactive Medications").

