The same definitions (only using invasive ventilation stop date/time and invasive ventilation breaks: FVS, PVS and other invasive) and analyses as described for the primary endpoint will be applied.

Length of PICU stay

The length of PICU stay will be calculated as the total number of days postoperative until discharge from PICU. The length will be derived as the number of days from day after surgery (variable "Date of surgery" on CRF "Surgery" + 1) until discharge from PICU (variable "Date transferred to floor" on CRF "Post-operative observation"). If subject has to be readmitted to PICU, time will continue to accrue (variables "Date of readmission" and "Date transferred to floor" (second assessment) from CRF "Post-operative observation").

- Length of PICU stay (days) =
(Date transferred to floor - (Date of surgery + 1) + 1) +
(Date transferred to floor (2nd assessment) - Date of readmission + 1)

For subjects who died before discharge from PICU or before Day 28, respectively, the observed length of PICU stay will be used. As sensitivity analyses subjects who died will (1) be excluded from analysis and (2) be assigned a length of PICU stay of 28 days.

For the length of PICU stay the same analyses as described for the primary endpoint will be applied.

Length of time on vasodilators

Length of time on vasodilators will be measured from first use following separation from bypass, until the subject is discharged from the hospital or at Day 28. The length will be derived as the time in minutes from separation from CPB (variable "End time" of parameter "CPB" from section "Post incision" on CRF "Surgery") until last use (last "end date/time" of any medication as documented in sections "Vasodilators" or "Other vasodilators" on CRF "Inotropes and Vasoactive Medications").

- Length of time of vasodilators (min) =
Last "end date/time" of any vasodilators - End time (CPB) + 1

Any interruptions will discontinue to accrue, any duration of re-use of vasodilators will continue to accrue. If a subject did not use any vasodilators the length is set to 0. As a sensitivity analysis, subjects with no use of vasodilators will be excluded. For subjects who died before discharge from the hospital or before Day 28, respectively, the observed length of time on vasodilators will be used. As sensitivity analyses subjects who died will (1) be excluded from analysis and (2) be assigned a length of time on vasodilators of 28 days.

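### The SAP's vasodilator formula contradicts its own text on start point and interruptions; programmed as printed, it gives time to last use, not time on drug

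*Protocol*

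**What the plan says.** Protocol 7.1.4 opens its vasodilator paragraph with "Length of time on vasodilators will be measured from first use following separation from bypass", running to discharge or Day 28. The next sentence sets a different origin: "The length will be derived as the time in hours from separation from CPB until discontinuation of all vasodilators". On repeat use it says only "Any duration of re-use of vasodilators will continue to accrue", and nothing about subtracting gaps. Protocol 6.2.1.6, on data collection, has "Use of vasodilators will be recorded from first use following separation from bypass".

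SAP 4.4.2 repeats the first-use sentence, again derives the length from CPB separation (now in minutes), and prints a formula: the last end date/time "of any vasodilators - End time (CPB) + 1". Directly below the formula it adds a rule that the Protocol lacks: "Any interruptions will discontinue to accrue, any duration of re-use of vasodilators will continue to accrue". Non-users are set to 0. The sensitivity analyses listed in that section exclude non-users or vary the handling of deaths. None varies the start point.

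**The concern.** The SAP section contains two internal conflicts.

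- **Start point.** One sentence starts the clock at first use, while the derivation and the formula start it at CPB separation. Protocol 7.1.4 has the same conflict.
- **Interruptions.** The text says they do not count, but the formula cannot remove them. This is not the SAP's general style. The ventilation formula in SAP 4.4.1 subtracts the "sum of all ventilation breaks with any ventilation break = Restart time - Stop time + 1", and the PICU and chest-tube formulas add separate episodes.

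A programmer cannot satisfy both the text and the printed line. Vasodilator usage and length of time on vasodilators form a secondary objective in both documents, and the arms are compared by a rank test at two-sided 5%. If the quantity analysed is time to last use, a child with one short, late infusion ranks as a long user.

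**Working it through.** The documents give no figure for vasodilator duration, so there is nothing to reproduce. The check applies each reading to the same use patterns.

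**Inputs.** The formula and interruption sentence come from SAP 4.4.2. The stop − start + 1 convention comes from SAP section 4. The break rule (restart − stop + 1) is borrowed from the ventilation formula in SAP 4.4.1. Use patterns in hours are assumptions. One clock pattern is borrowed from the dobutamine lines of the SAP's inotrope-score example: CPB separation at 12:00, then use at 13:00–13:30, 14:01–14:59 and 16:00–17:00, treated here as if it were a vasodilator.

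**Three readings, in minutes.**
- A, as printed: last end − CPB end + 1.
- B, printed formula with the interruption sentence applied: A − sum of (restart − stop + 1).
- C, time on drug: sum of (stop − start + 1) over treated intervals.

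| Use after CPB separation | A | B | C | A/C |
|---|---|---|---|---|
| 36–40 h | 2401 (40 h) | 2401 (40 h) | 241 (4 h) | 9.96 |
| 2–6 h and 90–94 h | 5641 (94 h) | 600 (10 h) | 482 (8 h) | 11.7 |
| 0–30 h, continuous | 1801 (30 h) | 1801 (30 h) | 1801 (30 h) | 1.00 |
| 1–25 h, continuous | 1501 | 1501 | 1441 | 1.04 |
| 0–6 h and 7–13 h | 781 | 720 | 722 | 1.08 |
| SAP clock pattern | 301 | 207 | 151 | 1.99 |

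**Second row in full.** A = 94 × 60 + 1 = 5641. The gap from 6 h to 90 h is 5040 + 1 = 5041, so B = 5641 − 5041 = 600. C = 241 + 241 = 482.

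**Last row in full.** A = 300 + 1 = 301. The breaks are 31 + 1 = 32 and 61 + 1 = 62, so B = 301 − 94 = 207. C = 31 + 59 + 61 = 151.

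**General relation.** With k treated intervals, A − C = delay before first use + total gap time − (k − 1) minutes. For the SAP pattern this is 60 + 92 − 2 = 150 = 301 − 151. Reading B removes the gaps but leaves the delay before first use.

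**Effect on ranks.** Under A or B, the child treated for 4 h at 36–40 h (score 40 h) ranks above the child treated continuously for 30 h (score 30 h). Under C the order reverses.

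**The case against.** The best defence is that the first-use sentence sets an observation window. It ends at discharge or Day 28, which is not the end of treatment, and it nearly repeats the recording rule in Protocol 6.2.1.6. The sentence that begins the derivation would then be the operative one, and it names CPB separation in both documents. That origin is shared with ventilation and intubation and gives the survival analyses a common time zero. The interruption sentence sits immediately below the formula and can be read as part of it; the inotrope definition in SAP 4.4.1 has the same layout.

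The window reading is possible. It does not supply the missing interruption term, and it still counts untreated hours before first use in a variable called length of time on vasodilators.

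Three stronger readings are tempting, and the documents do not support them.

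- **That late or intermittent users are greatly inflated.** The documents give no distribution of start times or gaps. The large ratios come from assumed patterns, and early, continuous use gives ratios close to 1.
- **That 94 h is what the plan would score.** That holds only if the SAP's own interruption sentence is ignored. With it, the score is 10 h.
- **That the SAP moved the origin without declaring it, as it did declare for inotropes.** For inotropes the Protocol derived first use to last use, so there was a change to list in SAP section 5. For vasodilators the Protocol already derived from CPB separation, so there was none.

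A first-use sensitivity analysis is written out for inotropes and not for vasodilators. The instruction to apply the primary endpoint's analyses might be taken to import one, but those analyses are worded for inotrope and ventilation start times.

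**Conclusion.** The point stands as a definitional conflict in an exploratory secondary endpoint. SAP 4.4.2 cannot be programmed so that the formula, the first-use sentence and the interruption sentence all hold. The start-point part does not depend on how literally the formula is read, because the derivation sentences themselves begin at CPB separation: 40 h against 4 h in the late-use example. The interruption part arises only if the formula is coded as printed: 94 h against 10 h in the repeat-use example.

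How much this would move the comparison between arms, or in which direction, cannot be worked out from the documents. SAP 4.4.2 classes all secondary analyses as exploratory, and vasodilator time does not enter the primary composite, so the primary test and the sample size are unaffected. The section should be corrected, but the point does not threaten the trial's main conclusion.

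**What to change.** In SAP 4.4.2, replace the formula with the sum of documented vasodilator intervals after CPB separation, taking the union across agents so that overlapping infusions count once. Time before first use and interruptions then do not accrue, and re-use does. Summing intervals also avoids a small artefact of the break rule, which removes two minutes too many per break (SAP pattern from first use: 241 − 94 = 147 min against 151 min on drug).

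Align the first-use and derivation sentences with this definition. Record it in SAP section 5, since it departs from the Protocol's derivation from CPB separation. Keep CPB separation to last use as a named sensitivity analysis.

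The cost is one formula, one entry in section 5 and one extra analysis. No new data should be needed. The SAP takes vasodilator end times from the case report form that also holds the inotropes, for which section 5 says exact start and end times are documented. That vasodilator start times are captured in the same way is a reasonable inference and should be confirmed.

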7.1.5 Safety Variables

Safety endpoints will be analyzed using the SAF.

Adverse Events

Pre-treatment adverse events and treatment adverse events will be analyzed separately. AEs will be summarized by system organ class (SOC) and preferred term (PT) according to Medical Dictionary for Regulatory Activities (MedDRA). The number of events, as well as the number and rate of affected subjects will be reported. AEs (SOC and PT) will also be summarized by seriousness, as well as by severity and relationship to study medication. No statistical testing procedures will be applied to the analysis of AEs. No statistical testing procedures will be applied to the analysis of AEs.

Incidence of Refractory Hypotension

Refractory hypotension is defined as a 20% drop in mean MAP below specific age-related criteria for more than 30 minutes. The number of subjects with any refractory hypotension from end of surgery until 48 hours will be compared between groups using Fishers' exact test. Additionally, a logistic regression analysis will be applied including factor treatment and site.

Laboratory Values (CBC with differential, serum creatinine and electrolytes & liver enzymes)

The absolute values, absolute and percentage changes from baseline will be tabulated using summary tables listing descriptive measurements for all observed time points. No statistical testing procedures will be applied to the analysis of laboratory values.

7.2 Initial Determination of Sample Size Estimate

The primary endpoint of this study is a composite variable consisting of the longer of either (1) length of time on mechanical ventilation or (2) length of inotrope use. The primary analysis will be the based on the full analysis set and will be conducted using a Wilcoxon-rank-sum test. As a sensitivity analysis, the primary endpoint variable will also be analyzed using survival analysis methods.

The results for the composite endpoint variable, with re-intubation periods included, from the Phase IB study, CIT-002-01, are shown in Table 2:

Table 2: Phase IB study (CIT-002-01) Composite endpoint results

	Mean (SD)		
	Placebo (N = 11)	Citrulline (N = 11)	Total (N = 22)
Composite endpoint	44.4 (63.62)	14.3 (14.06)	29.3 (47.54)

SD = standard deviation, N = number of patients.

Data source: Table 14.2.2.5.1.1, CIT-002-01 Clinical Study Report

The sample size calculation was calculated using nQuery 7.0. The common standard deviation (SD) was estimated to be 46.3 using the observed SDs of 64 and 14. Again, using an assumed SD of 50 and expected mean values of 44 for placebo and 14 for the L-citrulline group, the effect size is estimated as being 0.600, which yields a sample size of N=92 per group when applying a two-sided Wilcoxon-rank-sum test with a 0.01 significance level and a power of 90%.

The power is even larger than 90% when applying the Phase IB results of the composite endpoint variable with re-intubation periods excluded. Only one patient within the Placebo group was re-intubated, resulting in a lower mean composite endpoint value of 32 and a SD of 26.26.

To allow for subjects being enrolled but not assigned to the full analysis set, an overall N=95 subjects per group will be enrolled.

7.3 Sample Size Estimation Revision

A sample size re-estimation will be done as soon as the first 95 consecutively randomized full analysis set (FAS)-patients will have undertaken their Follow up visit (Day 28 or Hospital Discharge). (Refer to section 5.1.2.7 for details.)

7.4 Interim Analysis

One interim analysis is planned to be carried out when the first 95 consecutively randomized full analysis set (FAS)-patients (i.e. 50% of the planned patients) will have undertaken their Follow up visit (Day 28 or Hospital Discharge), data required for the analysis of the composite endpoint have been entered into the eCRF, and those data have been cleaned appropriately. Only a sample size re-estimation will be carried out during this interim analysis; no other statistical analyses will be conducted. The sample size re-estimation will be done by an independent, unblinded statistician following the same procedures and criteria as for the initial

sample estimate, as described in section 7.2. Only the results of the sample size re-estimation will be provided to Asklepion.

Only the re-estimated variance values will be used for sample re-calculation, while the assumed values will not be re-estimated but kept as described in Section 7.2.

In the event that the sample size re-estimation leads to a reduction of the sample size due to lower re-estimated variance compared to the assumed variance values, the sample size as currently planned will be kept, and not reduced, to ensure robust estimations for safety and efficacy variables.

If the trial is to be continued with the re-estimated sample size, an appropriate protocol amendment will be submitted to the FDA as soon as feasible.

Final analysis will be based on the population of all randomized patients without taking the sample size re-estimation results into consideration. Due to the fact that only the interim variance will be assessed, no alpha adjustment of statistical analyses is required.

8 Quality Assurance and Quality Control

8.1 Audit and Inspection

Investigator sites and study documentation may be subject to Quality Assurance (QA) audit during the course of the study by the sponsor, CRO or its nominated representative. In addition, inspections may be conducted by regulatory authorities at their discretion. It is important that the investigator(s) and their relevant personnel are available during audits or inspections and that sufficient time is devoted to the process.

8.2 Monitoring

Data for each subject will be recorded on an eCRF. Data collection must be completed for each subject for whom there is an informed consent form (ICF) and is administered IMP.

In accordance with current Good Clinical Practice (cGCP) and International Conference on Harmonisation (ICH) guidelines, the study monitor will carry out source document verification at regular intervals to ensure that the data collected in the eCRF are accurate and reliable. The frequency of monitoring visits will be determined by the rate of subject recruitment.

The following will be reviewed at these visits:

Asklepion GROWTH HEALTH INNOVATION

11 August 2017

- Compliance with the protocol.
- · Consent procedure.
- Source documents.
- AE procedures.
- Storage and accountability of materials.

The monitoring visits also provide the sponsor with the opportunity to ensure the investigator's obligations and all applicable ICH or health authority regulation requirements are being fulfilled.

The investigator must permit the monitor, the IRB/IEC, the sponsor's internal auditors and representatives from regulatory authorities direct access to all study-related documents and pertinent hospital or medical records for confirmation of data contained within the CRFs. Subject confidentiality will be protected at all times.

An electronic medical record may be the source document; however, the study site must provide a standard operating procedure(s) (SOPs) that details review and approval of data entries by the principal, investigator(s).

8.3 Data Management and Coding

The sponsor or CRO will be responsible for activities associated with the data management of this study. This will include setting up a relevant database and data transfer mechanisms, along with appropriate validation of data and resolution of queries. Data generated within this clinical study will be handled according to the relevant SOPs of the data management and biostatistics departments of sponsor or CRO.

For Electronic Data Capture (EDC):

Study sites will enter data directly into an EDC system by completing the eCRF via a secure internet connection. Data entered into the eCRF must be verifiable against source documents at the study site. Data to be recorded directly on the CRF (without prior written or electronic record) will be identified and the CRF will be considered the source document. Any changes to the data entered into an EDC system will be recorded in the audit trail and is Food and Drug Administration (FDA) Code of Federal Regulations (CFR) Title 21 Part 11 compliant.

Data entered into the eCRF will be validated as defined in the Data Validation Plan. Validation includes, but is not limited to, validity checks (for example range checks), consistency checks and customized checks (logical checks between variables to ensure that study data are accurately reported). A majority of edit checks will be triggered during data entry and will

Asklepion GROWTH HEALTH PINNOVATION

11 August 2017

therefore facilitate efficient "point of entry" data cleaning. CRO Clinical Data Management will perform both manual eCRF review and review of additional electronic edit checks to ensure that the data are complete, consistent and reasonable. The electronic edit checks will run continually throughout the course of the study and the issues will be reviewed manually online to determine what action needs to be taken.

Manual queries may be added to the system by Clinical Data Management or Clinical Research Associates (CRAs). Data Managers and CRAs are able to remotely and proactively monitor the subject eCRFs to improve data quality.

CRO or designee will be responsible for:

- eCRF database creation and validation
- eCRF review and data validation

Medical coding will use MedDRA for concomitant diseases and adverse events and WHODrug for therapies.

Prior to the creation of a site data archive, it is necessary to be sure the database for the study in question has been closed. As an EDC system is being utilized for the study, CRO resources will produce the site data archives and deliver these archives to the study sites. Site data archive shall include not only an archive of the data entered, but also a record of the audit trail and any electronically created queries and comments. The site archival material shall be produced separately for each study site and then each set of materials or CDs should then be delivered to the study site for archival.

All study materials will be returned to the sponsor within a pre-agreed time interval from final database approval. The CRO clinical database (SAS), along with the SAS programs, will be stored on the CRO computer for a period of time to be agreed with the sponsor following completion of all activities due to be carried out for sponsor for the study prior to archiving. The archived electronic file will be destroyed after a pre-agreed period of time.

Missing or inconsistent data will be queried for clarification. Subsequent modifications to the database will be documented.

9 Records and Supplies

